**Withdrawal of consent:**

Subjects who request to discontinue receipt of study treatment will remain in the study and must continue to be followed for protocol-specified follow-up procedures. The only exception to this is when a subject specifically withdraws consent for any further contact with him or her or persons previously authorized by the subject to provide this information. Subjects should notify the investigator in writing of the decision to withdraw consent from future follow-up, whenever possible. The withdrawal of consent should be explained in detail in the medical records by the investigator, as to whether the withdrawal is only from further receipt of investigational product or also from study procedures and/or posttreatment study follow-up, and entered on the appropriate case report form (CRF) page. In the event that vital status (whether the subject is alive or dead) is being measured, publicly available information should be used to determine vital status only as appropriately directed in accordance with local law.

If the subject withdraws from the study and also withdraws consent for disclosure of future information, no further evaluations should be performed and no additional data should be collected. The sponsor may retain and continue to use any data collected before such withdrawal of consent.

**Lost to follow-up:**

If a subject does not return for a scheduled visit, every effort should be made to contact the subject. The investigator or site staff should attempt to contact the subject twice. After 2 attempts, CRU staff may send a registered letter. If no response is received from the subject, the subject will be considered lost to follow-up. All attempts to contact the subject and information received during contact attempts must be documented in the subject's medical record. In any circumstance, every effort should be made to document subject outcome, if possible. The investigator should inquire about the reason for withdrawal, request that the subject return all unused investigational product(s), request that the subject return for a final visit, if applicable, and follow up with the subject regarding any unresolved AEs.

All reasonable efforts must be made to locate subjects to determine and report their ongoing status. This includes follow-up with persons authorized by the subject as noted above. All attempts should be documented in the subject's medical records. If it is determined that the subject has died, the site will use locally permissible methods to obtain the date and cause of death. If the investigator's use of a third-party representative to assist in the follow-up portion of the study has been included in the subject's informed consent, then the investigator may use a sponsor-retained third-party representative to assist site staff with obtaining the subject's contact information or other public vital status data necessary to complete the follow-up portion of the study. The site staff and representative will consult publicly available sources, such as public health registries and databases, in order to obtain updated contact information. If, after all attempts, the subject remains lost to follow-up, then the last-known-alive date as determined by the investigator should be reported and documented in the subject's medical records.

## **7. ASSESSMENTS**

Every effort should be made to ensure that protocol-required tests and procedures are completed as described. However, it is anticipated that from time to time there may be circumstances outside the control of the investigator that may make it unfeasible to perform the test. In these cases, the investigator must take all steps necessary to ensure the safety and well-being of the subject. When a protocol-required test cannot be performed, the investigator will document the reason for the missed test and any corrective and preventive actions that he or she has taken to ensure that required processes are adhered to as soon as possible. The study team must be informed of these incidents in a timely manner.

For samples being collected and shipped, detailed collection, processing, storage, and shipment instructions and contact information will be provided to the investigator site prior to initiation of the study.

### **7.1. Safety**

#### **7.1.1. Laboratory Tests**

The following safety laboratory tests will be performed at times defined in the [STUDY PROCEDURES](#) section of this protocol. Additional laboratory results may be reported on these samples as a result of the method of analysis or the type of analyzer used by the clinical laboratory; or as derived from calculated values. These additional tests would not require additional collection of blood. Unscheduled clinical labs may be obtained at any time during the study to assess any perceived safety concerns.

**Table 7. Laboratory Tests**

Hematology	Chemistry	*Urinalysis	Other
Hemoglobin Hematocrit RBC count MCV MCH MCHC Platelet count WBC count Total neutrophils (Abs) Eosinophils (Abs) Monocytes (Abs) Basophils (Abs) Lymphocytes (Abs) Reticulocytes (%)	BUN/urea and Creatinine Glucose (fasting) Calcium Sodium Potassium Chloride Total CO 2 (Bicarbonate) AST, ALT Total Bilirubin Alkaline phosphatase Uric acid Albumin Total protein Serum Cystatin C Creatinine phosphokinase (for psoriasis subjects only)	pH Glucose (qualified) Protein (qualified) Blood (qualified) Ketones Nitrites Leukocyte esterase Urobilinogen Urine bilirubin Microscopy a	FSH b Urine drug screening c CCI Fibrinogen Lipids: TC, TG, LDLc, HDL Interferon Gamma Release Assay (IGRA) (with the following acceptable assays: QuantiFERON R -TB Gold (QFT-G) test, T-SPOT TB, QuantiFERON-TB Gold In-Tube test (QFT-GIT) f  HIV, HepBsAg, HepBcAb, HCVAb f  CCI  PK 6β-hydroxy cortisol CCI  CCI  CCI
	Additional Tests e (Needed for Hy's law)	Other :	
	AST, ALT (repeat) Total bilirubin (repeat) Albumin (repeat) Alkaline phosphatase (repeat) Direct bilirubin Indirect bilirubin Creatine kinase GGT PT/INR Total bile acids Acetaminophen drug and/or protein adduct levels	Urine for 24 hour creatinine clearance and CCI	

- a. Only if urine dipstick is positive for blood, protein, nitrites or leukocyte esterase.  
 b. At Screening only, in females who are amenorrheic for at least 12 consecutive months.  
 c. At Screening and pre-dose only (see [Schedule of Activities](#)). Minimum requirement for drug testing includes: cocaine, tetrahydrocannabinol (THC), opiates/opioids, benzodiazepines and amphetamines.

CCI

- e. Additional testing for potential Hy's Law cases only.
- f. Screening only. All subjects will be screened for HBsAg and HBcAb; subjects who are HBsAg positive will be screen-failed. Subjects who are HBsAg negative but HBcAb positive will be reflex-tested for HBsAb and, if HBsAb positive, may enroll; if HBsAb negative, they will be screen-failed. Subjects who are positive for HCV Ab or HIV will be screen-failed.

**C**  
**C**

- \* Urinalysis sample may also be used to assess additional markers of renal function.

**This table lists all protocol laboratory tests included in the study. For a detailed description of laboratory tests required for a given subject cohort with specific collection time points, please refer to the [Schedule of Activities](#).**

- Minimum requirement for drug testing includes: cocaine, THC, opiates/opioids, benzodiazepines and amphetamines.
- Subjects may undergo random urine drug screening at the discretion of the investigator. Drug screening conducted prior to dosing must be negative for subjects to receive study medication.

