spleen, and lymph node (mesenteric) in monkeys at  $\geq 150$  mg/kg/day. This finding was associated with nondose-related lower or decreased lymphocyte, white blood count (WBC), and/or eosinophil counts in rats and monkeys at  $\geq 30$  mg/kg/day. Additionally, lower reticulocyte numbers were observed in rats at  $\geq 30$  (15 twice a day (BID) mg/kg/day and not associated with any adverse effects in red blood cell (RBC) mass parameters. Further observations included lower numbers of T cells, B cells, NK cells, and absolute lymphocyte counts in peripheral blood and/or spleen of rats at  $\geq 30$  (15 BID) mg/kg/day for cytotoxic T cells and NK cells in spleen or  $\geq 200$  (100 BID) mg/kg/day for all other PF-06826647-related immunophenotyping parameters. In monkeys, decreased numbers of T cells in peripheral blood and NK cells in peripheral blood and spleen occurred at  $\geq 30$  mg/kg/day, and decreased number of T cells, B cells, and absolute lymphocytes occurred in the spleen at 300 mg/kg/day. Minimal decreased cellularity in all cell lineages was observed in the bone marrow (sternum) of monkeys at  $\geq 150$  mg/kg/day and corresponded with decreased RBC mass parameters (red blood cell (RBC), hemoglobin (HGB), and hematocrit (HCT)), reticulocytes, and WBC counts at  $\geq 30$  mg/kg/day. The findings in the thymus, spleen, lymph nodes, bone marrow, erythron, and leukon observed in rats and monkeys are consistent with the pharmacological activity of PF-06826647, and were not adverse due to their low magnitude/severity of the effects and/or because they were not associated with any clinical or microscopic evidence suggestive of PF-06826647-related infections in these animals.

PF-06826647-related higher or increased alanine transaminase (ALT), aspartate aminotransferase (AST), alkaline phosphatase (ALP), and/or triglycerides were observed in rats at  $\geq 30$  (15 BID) mg/kg/day and in monkeys at  $\geq 30$  mg/kg/day. Additionally, higher cholesterol was observed in rats at 500 (250 BID) mg/kg/day. None of these alterations were adverse due to their minor magnitude and the absence of correlating microscopic findings.

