PF-06826647-related nonadverse minimally higher femoral metaphyseal medullary trabecular bone thickness was observed in the bone of the stifle joint in rats at 500 mg/kg/day after 14 days of repeated administration, but not at the same dose in the 1-month study. The growth plate was within normal limits, and no evidence of inflammation, necrosis, or hemorrhage of the medullary trabecular bone was noted. This effect on bone was not observed in monkeys.

Other nonadverse PF-06826647-related findings included clinical observations, body weights, and/or clinical pathology parameters that lacked in-life or post-mortem correlates and/or were minor in magnitude. These included higher mean fibrinogen in rats at  $\geq 200$  (100 BID) mg/kg/day; higher mean total protein, consisting of both higher mean albumin and globulin, in rats at 500 (250 BID) mg/kg/day; dose-dependent, lower mean body weight gain and mean absolute body weight in rats at  $\geq 30$  (15 BID) mg/kg/day; decreased phosphorus in monkeys at  $\geq 30$  mg/kg/day; and pale/white discolored feces in monkeys at  $\geq 100$  mg/kg/day.

The no-observed-adverse-effect-level (NOAELs) in the 1-month pivotal rat and monkey toxicity studies were 500 (250 BID) mg/kg/day in rats (unbound  $C_{\max}$  = 1870 ng/mL and  $AUC_{24}$  = 16,600 ng•h/mL) and 300 mg/kg/day in cynomolgus monkeys (unbound  $C_{\max}$  = 1790 ng/mL and  $AUC_{24}$  = 19,900 ng•h/mL). Exposures at these doses were 28x to 36x the predicted human efficacious unbound exposures ( $C_{\max}$  and  $AUC_{24}$ ).

The nonclinical safety profile of PF-06826647 has been adequately characterized to support progression into clinical trials of up to 4 weeks

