Subjects should return to the investigational site and be evaluated as soon as possible, **preferably within 24-48-hours** from awareness of the abnormal eGFR result. This evaluation should include laboratory tests, detailed history, and physical assessment. In addition to evaluating eGFR as calculated by sCr and S Cystatin C, laboratory tests should include: serum blood-urea-nitrogen, serum creatine kinase, serum electrolytes (including at a minimum potassium, sodium, phosphate/phosphorus, calcium), in addition to urinary dipstick, urine microscopic examination, and urinary indices. All cases confirmed on repeat testing as meeting the eGFR criteria for acute-kidney-injury, with no other cause(s) of laboratory abnormalities identified should be considered as potential cases of drug-induced kidney injury irrespective of availability of all the results of the investigations performed to determine etiology of the abnormal sCr. If  $\geq 2$  healthy subjects in a given cohort are noted to have 2 *consecutive* decreases from baseline in eGFR of  $\geq 30\%$ , based on both sCr AND S Cystatin C, an assessment of whether the finding may be considered adverse drug reaction should be undertaken.

This requirement applies to all subjects, all cohorts.

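### Phosphorus fell in monkeys, but Table 7 neither measures it nor lets one derive it, so the laboratory-safety endpoint is not set up to detect such a fall routinely

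*Protocol*

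**What the plan says.** Protocol Section 1.2.4 lists the clinical-pathology changes seen in rats and monkeys. Among them is "decreased phosphorus in monkeys at" 30 mg/kg/day and above. The protocol puts this in a group of nonadverse findings that "lacked in-life or post-mortem correlates and/or were minor in magnitude".

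The Chemistry column of Table 7 (Section 7.1.1) is unredacted. Its electrolyte part reads "Glucose (fasting) Calcium Sodium Potassium Chloride", followed by bicarbonate; neither phosphorus nor phosphate appears anywhere in the column. The note under the table states: "This table lists all protocol laboratory tests included in the study".

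Section 7.12.1 requires, in the evaluation of a potential acute kidney injury, "serum electrolytes (including at a minimum potassium, sodium, phosphate/phosphorus, calcium", and applies this to all subjects and cohorts. Section 7.1.1 also permits extra results that the analyser happens to produce and unscheduled tests for a perceived safety concern, but requires neither.

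The primary endpoint in both the healthy and psoriasis segments (Protocol Section 2) includes the incidence and magnitude of treatment-emergent laboratory abnormalities, chemistry among them. SAP Section 6.3.2 takes its tests from the protocol and adds none. SAP Section 8.4.5 summarizes laboratory data by treatment and plots mean change from baseline.

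**The concern.** A first-in-human laboratory panel is normally checked against the animal findings, so that each drug-related signal has a matching scheduled test. Here that match has one gap. If phosphorus fell in treated subjects, no scheduled test would show it, and a chemistry summary without abnormalities would say nothing about phosphorus.

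The protocol's nonadverse label does not explain the omission. Higher fibrinogen (rats, 200 mg/kg/day and above) and higher total protein and albumin (rats, 500 mg/kg/day) carry the same label, and all three are measured. Fibrinogen even has its own row in the healthy-subject schedules and is named in that segment's primary endpoint. The phosphorus change was reported from 30 mg/kg/day, the lowest monkey dose in the readable text, so no unaffected monkey dose is described. No reason is given for leaving it out.

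There is also an internal conflict. A table described as complete omits an analyte that another section makes mandatory. Table 7 has a block for the triggered Hy's law tests but none for the triggered kidney tests. A phosphate value obtained in a kidney work-up would have no assured baseline.

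**Working it through.** The plan gives no figure of its own on this point. The check has two parts: matching findings to tests, then comparing exposures.

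**Part 1. Toxicology blood-chemistry signals (Section 1.2.4) against Table 7**

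| Signal | In Table 7? |
|---|---|
| ALT, AST, ALP, triglycerides ("alkaline phosphatase (ALP), and/or triglycerides were observed in rats at" 30 mg/kg/day and above; also in monkeys) | Yes, all four |
| Cholesterol ("higher cholesterol was observed in rats at 500 (250 BID) mg/kg/day") | Yes |
| Fibrinogen | Yes (Other column) |
| Total protein and albumin ("consisting of both higher mean albumin and globulin") | Yes, both |
| Globulin | Not listed; equals total protein minus albumin |
| Phosphorus | Not listed; not derivable |

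Count: 4 + 1 + 1 + 2 = 8 measured, 1 derivable, 1 neither; 10 in all. Phosphorus measurements required on schedule: 0. Elsewhere in the two documents phosphorus appears as a study test only in Section 7.12.1.

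**Part 2. Could human exposure reach the level at which the fall was reported?**

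Inputs:
- Monkey free AUC24 at 300 mg/kg/day: 19,900 ng.h/mL (Section 1.2.4).
- Monkey exposure rose less than dose-proportionally up to 300 mg/kg/day (Section 1.2.3). Exposure at 30 mg/kg/day is not given.
- Human unbound fraction: 0.38 (Table 3 footnote).
- Human total AUC24, preliminary geometric means: 9321 after a single 1600 mg dose, fasted (Table 1); 1950 at 100 mg QD and 4919 at 400 mg QD on Day 10, fed (Table 2). The 400 mg value is partial data from 4 subjects.

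Monkey range at 30 mg/kg/day. Strict proportionality gives the floor, 19,900 × 30/300 = 1,990. No increase with dose gives the ceiling, 19,900. The true value lies between them.

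Human free AUC24 = total × 0.38:
- 400 mg QD: 4919 × 0.38 = 1,869.
- Single 1600 mg: 9321 × 0.38 = 3,542.
- 1200 mg QD, if linear from 400 mg (assumption): 1,869 × 3 ≈ 5,600.
- 1200 mg QD, if the 100 to 400 mg trend continues (assumption): exponent = ln(4919/1950)/ln 4 = 0.67; 3^0.67 ≈ 2.08; 1,869 × 2.08 ≈ 3,900.

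| Human dose | Free AUC24 (ng.h/mL) | Ratio to ceiling (19,900) | Ratio to floor (1,990) |
|---|---|---|---|
| 400 mg QD | 1,869 | 0.09 | 0.94 |
| 1600 mg single | 3,542 | 0.18 | 1.8 |
| 1200 mg QD, trend | about 3,900 | 0.2 | 2.0 |
| 1200 mg QD, linear | about 5,600 | 0.28 | 2.8 |

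At 400 mg QD the mean is below even the floor, so overlap is not shown. At the higher doses the ratio spans 1, so overlap is neither shown nor excluded.

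**The case against.** The case on the other side is substantial, and most of it limits the point rather than removing it.

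- **The finding is nonadverse.** The protocol says so, and the monkey NOAEL was 300 mg/kg/day, ten times the dose at which the fall begins. This stands, and it lowers the weight. It does not explain why equally nonadverse signals are measured and this one is not.
- **Phosphorus could still be seen.** A reader might infer that the endpoint cannot detect a fall at all. The documents do not support that: Section 7.1.1 allows incidental and unscheduled results, and Section 7.12.1 mandates phosphate in a kidney work-up. These routes are optional or triggered, so they give no assured baseline and no systematic comparison with placebo.
- **The kidney link.** A reader might treat the monkey finding as a renal signal, because the protocol adds cystatin C and creatinine clearance. No text connects the two. Cystatin C is there because MATE2K inhibition may affect creatinine transport, the listed target organs do not include the kidney, and a potential kidney injury is decided on creatinine- and cystatin-based eGFR. Some Hy's law tests, such as GGT and PT/INR, also lack a scheduled baseline. The missing baseline is an inconvenience and would not change how a case is classified.
- **Exposure.** A reader might infer overlap at the 400 mg dose planned for the first psoriasis cohort. The figures do not show it. A linear step to 1200 mg QD is also uncertain: Section 1.3.2 describes steady-state exposure as less than dose-proportional, although single doses looked linear from 400 to 1600 mg.
- **Redaction.** Parts of Table 7's Other column are blacked out, so a hidden entry cannot be wholly excluded. The Chemistry column, where phosphate would belong, is intact.

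**Conclusion.** The gap is real and minor. Phosphorus is the only readable toxicology blood-chemistry signal that Table 7 neither measures nor allows to be derived, so the primary laboratory-safety endpoint is not set up to detect a fall routinely. Separately, the statement that Table 7 is complete and the phosphate requirement in Section 7.12.1 conflict and must be reconciled, however the monkey finding is weighed.

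It would go too far to say that the primary endpoint is compromised or that a safety risk has been missed. The endpoint covers chemistry as Table 7 defines it; it simply leaves out one known signal of low weight. The relevance to humans rests on an unknown, the monkey exposure at 30 mg/kg/day, for which only the range 1,990 to 19,900 ng.h/mL can be given, and on preliminary human data.

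The practical reach is limited to subjects not yet dosed. By 25 March 2018, before Amendment 3, six SAD and three MAD cohorts (53 healthy subjects) had completed dosing (Section 1.3.2). Still to come, assuming nothing further had started, were the highest-dose MAD cohort, the optional cohorts, and about 42 psoriasis subjects with 28 days of treatment, the longest in the study.

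**What to change.** 1. Add inorganic phosphorus to the Chemistry column of Table 7, at every scheduled chemistry draw including baseline, for all cohorts still to be dosed: the remaining MAD cohort, any optional cohorts, and both psoriasis cohorts.
2. Include it in the SAP Section 8.4.5 laboratory summaries and change-from-baseline plots.
3. Reconcile Table 7 with Section 7.12.1, for example by adding a block for the triggered kidney-injury tests like the existing Hy's law block.

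Cost: one more analyte on the chemistry sample already drawn, with no extra visit or procedure and, assuming the present tube suffices, no extra blood. There is one more laboratory variable to report. Cohorts already completed will contribute no phosphorus data, and the report should say so.

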### **7.1.2. Pregnancy Testing**

All pregnancy tests used in this study, either urine or serum, must have a sensitivity of at least 25 mIU/mL and must be performed by a certified laboratory. For female subjects of childbearing potential, 2 negative pregnancy tests are required before receiving investigational product/study treatment(s) (1 negative pregnancy test at screening and 1 at the baseline visit immediately before investigational product/study treatment administration). Following a negative pregnancy test result at screening, appropriate contraception must be commenced and the second negative pregnancy test result will then be required at the baseline visit and within 5 days after the first day of the menstrual period (counting the first day of the menstrual period as Day 1) before the subject may receive the investigational product/study treatment. In the absence of regular menstrual bleeding, the study candidate should have used 2 forms of contraception for at least 1 month before the second pregnancy test. Pregnancy tests will also be repeated at every visit and at the end of the study to confirm that the subject has not become pregnant during the study. Pregnancy tests will also be done whenever 1 menstrual cycle is missed during the active treatment period and when potential pregnancy is otherwise suspected, and may be repeated if requested by institutional review boards (IRBs)/ethics committees (ECs) or if required by local regulations. In the case of a positive confirmed pregnancy, the subject will be withdrawn from administration of investigational product and from the study.

### **7.1.3. Physical Examinations**

Physical examinations may be conducted by a physician, trained physician assistant, or nurse practitioner as acceptable according to local regulation. A full physical examination will include head, ears, eyes, nose, mouth, skin, heart and lung examinations, lymph nodes, gastrointestinal, musculoskeletal, and neurological systems. The limited or abbreviated physical examination will be focused on general appearance, the respiratory and cardiovascular systems, as well as towards subject reported symptoms.

For measuring weight, a scale with appropriate range and resolution is used and must be placed on a stable, flat surface. Subjects must remove shoes, bulky layers of clothing, and jackets so that only light clothing remains. They must also remove the contents of their pockets and remain still during measurement of weight.

